3.3.4.1.2 Dog GLP Toxicology Study

A GLP study assessed the potential toxicology and toxicokinetics of LSALT peptide when administered by intravenous infusion to Beagle dogs once daily for 14 days. The control group was administered the vehicle used to prepare the LSALT peptide dosing formulations (0.9% sodium chloride, USP). Three dose groups of 2.5, 7.5, and 15 mg/kg were evaluated. The LSALT peptide dose formulation and the control vehicle were administered to animals by intravenous infusion at a dose volume of 2 mL/kg based on the most recent body weight of each animal. The progression or regression of any effects was evaluated during an additional 14-day treatment-free, recovery period in the control and high dose groups.

LSALT peptide administered to Beagle dogs by daily intravenous infusions for 14 days in the dose range of 2.5 to 7.5 mg/kg was well tolerated with no test-item related clinical observations noted.

The dose level of 15 mg/kg resulted in manifestation of pseudo-allergic (anaphylactoid) infusion reactions. The clinical signs appeared shortly after dosing and consisted of reddening of the skin around the eyes and mouth, head flicking, facial edema, hives/reddening on the pinnae, and/or reddened eyes and muzzle. Pseudo-allergic reactions were typically observed throughout the entire treatment phase duration. Affected animals were treated with diphenhydramine by IV injection. These reactions occurred during infusion and disappeared shortly after the infusion was completed. Other clinical signs were sporadic and not considered to be related to treatment with the test item. These reactions may likely diminish by lengthening the time of infusion for delivering daily doses ≥ 15 mg/kg.

Pseudo-allergic reactions following intravenous administration of peptides/proteins in dogs have been reported and occur in response to the infusion of biotherapeutics. Non-clinical infusion reactions do not necessarily predict responses in humans (Mease *et al*, 2017; Cohn *et al*, 2007; Roselló *et al*, 2017).

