3.3.6 Pharmacokinetics

Figure 5. Intact LSALT peptide 5 mg single and multiple dose plasma concentrations

As seen in Figure 5, there was rapid elimination of intact LSALT peptide after the end of the infusion (2 hours) with an estimated mean \pm SD $t_{1/2}$ of 0.41 ± 0.147 and 0.21 ± 0.0753 hours for the single dose and multiple dose, respectively. Apparent clearance was 580 ± 155 and 990 ± 146 L/hr for the two regimens.

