7.3.2.4 Cardiovascular Assessments

Vital signs including supine pulse rate and blood pressure will be measured at Screening, and on Days 3, EOT, and EOS. ECGs (12-lead) will be recorded at Baseline pre-dose, Day 3, EOT, and at EOS (if clinically indicated). Highly-sensitive troponin levels will be compared from baseline and between treatment groups throughout the study (refer above to Section 7.3.2.3).

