8 STUDY PROCEDURES AND FLOW CHART

8.1 Study Flow Chart

Calendar	Admission ^a	Admission ^b	Treatment Period	Treatment Period	EOT	EOS
Day	1	1	1 – 14 (max)	3	Variable	28±3
Sign informed consent	X					
Assign screening number	X					
Inclusion/exclusion criteria	X					
Review demographics	X					
Review medical history	X					
Concomitant meds ^c	X		X	X	X	X
Physical exam ^c	X		X	X	X	X
Respiratory exam ^c	X		X	X	X	X
Urine pregnancy in WCBP	X					
Clinical labs/Urine tests ^{c,d}	X			X	X	X
12-lead ECG ^e	X			X	X	X
Vital signs ^{c,f}	X		X	X	X	X
eGFR ^{b,d}	X			X	X	X
SARS-CoV-2 testing swabs ^{c,g}	X			X	X	X
Chest x-ray ^h		X		X	X	X
PK and biomarker samples ⁱ		X		X	X	X
Randomization		X				
Study drug administration		X	X	X	X	X
AE assessments		X	X	X	X	X
SARS-CoV-2 IgG, IgA, IgM levels		X				X
Berlin Definition ^{j,k}		X		X	X	X
SOFA score ^{j,l}		X		X	X	X
mMRC score ^{j,m}		X		X	X	X
APACHE II score ^{j,n}		X		X	X	X
Health Outcomes						X

^a Screening to determine eligibility (prior to randomization)

^b Baseline after Screening and prior to the start of study drug unless otherwise indicated.

^c Performed at Screening, Day 3, and EOT prior to drug administration, and at EOS.

^d Hematology, biochemistry, coagulation, and urinalysis will be obtained and eGFR will be calculated (Appendix 2), and when clinically indicated.

^e 12-Lead ECG (supine) will be recorded at time 0 (pre-dose) at Screening, Day 3, EOT, and at EOS (only if clinically indicated). Also, an ECG will be obtained during the study when clinically indicated.

^f Blood pressure (supine), pulse rate (supine), body temperature, respiration rate (supine), actual body weight (kg), and height (cm). Note: Height will only be measured at Screening.

^g Swabs (nasal, throat, sputum, or lower respiratory tract) at Screening, Day 3, EOT, and EOS.

^h Chest x-rays at Baseline (Day 1), Day 3, at time of clinical improvement, at EOT, and EOS. A chest x-ray will also be obtained if clinically warranted and recorded in the eCRF.

ⁱ Blood draws at Baseline pre-dose, at the mid-point (1 hr) and at the end of 2-hr infusion of study drug on Days 1, 3, and EOT, and a single blood draw at EOS.

^j Obtained at Baseline, Day 3, when clinically indicated, at EOT, and at EOS.

^k Appendix 3

^l Appendix 4

^m Appendix 5

ⁿ Appendix 6

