8.2.2 Baseline Visit (Day 1b)

- Obtain chest x-ray
- Collect blood samples (5 mL each) at Baseline prior to start of drug infusion, at one hour post start of infusion, and end of the daily 2-hour drug infusion for PK, cytokines, and antibody analysis. Prepare the samples per Section 7.3.2.2.
- Review and record any TEAEs
- Complete the (1) Berlin Definition (Appendix 3), (2) SOFA score (Appendix 4), (3) modified Medical Research Council Dyspnea Scale (Appendix 5), and (4) APACHE II score (Appendix 6) pre-dose.
- Randomize the patient
- Administer IV drug over 2 hours (after completion of all other assessments and procedures on Day 1)

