8.2.3 During Treatment Period (Days 1, 2, 4 – 14 (maximum))

- Document concomitant drugs, including drug name, dose, and frequency

- Perform physical examination including respiratory exam
- Measure vital signs, including blood pressure (sitting), pulse rate, body temperature, respiration rate, and actual body weight (kg) daily or as clinically indicated – note: no need to document height.
- Administer IV drug over 2 hours
- Review and record any TEAEs.

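### Scheduled ECGs and vital signs are either pre-dose (Day 3, and EOT under the flow-chart footnotes) or untimed, so their tables say little about transient, asymptomatic effects at peak exposure.

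*Combined protocol and SAP*

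**What the plan says.** All references are to the protocol.

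- **ECG.** Section 8.1, footnote e: "12-Lead ECG (supine) will be recorded at time 0 (pre-dose) at Screening, Day 3, EOT". The EOS ECG is done only if clinically indicated. Unscheduled ECGs are allowed on the same ground.
- **Vital signs, Day 3 and EOT.** Footnote c, attached to the vital-signs row: "Performed at Screening, Day 3, and EOT prior to drug administration, and at EOS".
- **Vital signs, other treatment days.** Section 8.2.3 (Days 1, 2 and 4 to 14) asks for "Measure vital signs, including blood pressure (sitting), pulse rate, body temperature" and other measures, daily or when clinically indicated. It gives no time relative to the infusion.
- **Day 1 order.** Section 8.2.2: "Administer IV drug over 2 hours (after completion of all other assessments and procedures on Day 1".
- **Timed contacts that already exist.** Section 7.3.2.2 and footnote i require blood draws at 1 hour and at the end of the 2-hour infusion on Days 1, 3 and EOT.
- **EOT.** Section 8.2.5 ties the EOT visit to completion of the last dose.
- **Body position.** Section 7.3.2.4: "Vital signs including supine pulse rate and blood pressure will be measured at Screening, and on Days 3, EOT, and EOS". Footnote f also says supine. Sections 8.2.1, 8.2.3, 8.2.4 and 8.2.6 say sitting.
- **Use of the data.** Vital signs and ECG are safety endpoints (Section 4.2.5). They are assessed as changes from baseline (Section 7.3) and summarised by treatment (Section 9.3.4.3).

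**The concern.** Section 3.3.6 describes "rapid elimination of intact LSALT peptide after the end of the infusion (2 hours"), so exposure to intact peptide is confined largely to the infusion and a short period after it. The one treatment-related clinical toxicity described in the 14-day animal studies, the pseudo-allergic reaction in dogs, had the same time course: "These reactions occurred during infusion and disappeared shortly after the infusion was completed". A drug with this profile is most likely to show an acute effect on pulse, blood pressure, respiration or ECG intervals while it is running. The plan places its fixed-time measurements at the opposite end of the dosing interval.

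This matters because Section 9.1 bases the sample size of 60 partly on a wish to assess safety. Earlier human multiple dosing, as described in Section 3.3.5, was 5 mg daily for 3 days; this trial doses hospitalised patients for up to 14 days. Flat ECG and vital-sign tables could be taken as evidence of acute tolerability when the measurements were not placed to show it.

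**Working it through.** The plan states no gap or half-life count, so there is no figure of its own to reproduce.

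**Inputs**
- Infusion 2 h, once daily at a consistent time (Section 6.2).
- Half-life of intact peptide, mean (SD): 0.41 h (0.147) and 0.21 h (0.0753) "hours for the single dose and multiple dose, respectively" (Section 3.3.6).
- Missed-dose rule (Section 6.2): a late dose may be given up to 8 h before the next one. The gap between infusions can then be 6 to 8 h, depending on whether the 8 h runs from the start or the end of the late infusion.

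**Formulas.** Gap = dosing interval − infusion time. Half-lives elapsed = gap / t½. Fraction left = 0.5^(gap / t½), assuming simple exponential decline.

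**Usual gap:** 24 − 2 = 22 h.

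| t½ used | Half-lives in 22 h | Fraction left |
|---|---|---|
| Single dose, mean 0.41 h | 22/0.41 = 53.7 | about 7 × 10⁻¹⁷ |
| Single dose, +1 SD, 0.557 h | 39.5 | about 1 × 10⁻¹² |
| Single dose, +2 SD, 0.704 h | 31.3 | about 4 × 10⁻¹⁰ |
| Multiple dose, mean 0.21 h | 22/0.21 = 104.8 | about 3 × 10⁻³² |
| Multiple dose, +2 SD, 0.3606 h | 61.0 | about 4 × 10⁻¹⁹ |

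**After a late dose:** a 6 to 8 h gap gives 14.6 to 19.5 half-lives at 0.41 h and 28.6 to 38.1 at 0.21 h. The least favourable case is 6 h with t½ 0.704 h: 8.5 half-lives, about 0.3% left.

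**End of infusion:** 2/0.41 = 4.9 and 2/0.21 = 9.5 half-lives after the start. Under the same assumption the level is 1 − 0.5^4.9 ≈ 97% of plateau or higher, so the 2 h draw sits essentially at peak.

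**What each scheduled measurement can see**

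| Occasion | ECG | Vital signs |
|---|---|---|
| Day 1 | Pre-dose baseline | Pre-dose baseline; further Day 1 values in 8.2.3 untimed |
| Day 3 | Pre-dose (footnote e) | Pre-dose (footnote c) |
| Days 2, 4 to 14 | None scheduled, except at EOT | Untimed (8.2.3) |
| EOT | Pre-dose by footnote e; after the last dose by 8.2.5 | Pre-dose by footnote c; after the last dose by 8.2.5 |
| During infusion or at its end | None | None |

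The Day 3 result is firm. The EOT result holds only if sites follow the footnotes. If some follow Section 8.2.5 instead, the EOT tables will mix trough and post-infusion values. On the other days the fault is a missing time, so those values cannot be placed against exposure from what the protocol requires.

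**The case against.** The case for leaving the schedule alone has real force.

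- **The animal signal is remote.** The dog reactions occurred at 15 mg/kg; 2.5 to 7.5 mg/kg was well tolerated. Section 3.5 converts 2.5 mg/kg in dogs to 1.4 mg/kg in humans, so 15 mg/kg corresponds to 15 × 1.4/2.5 = 8.4 mg/kg. The study dose is 5/70 = 0.071 mg/kg, about 118 times lower. The signs were mainly skin and facial, which an ECG would not show. Section 3.3.4.1.2 reports no vital-sign differences from control dogs and says such reactions need not predict human responses. Section 3.3.5 reports no drug-related clinical adverse events in people.
- **Other routes of detection exist.** Infusions are supervised, adverse events are reviewed on every treatment day, and ECGs and vital signs can be taken when clinically indicated.
- **Pre-dose timing is coherent** for finding persistent effects and matches the pre-dose baseline.

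These points defeat three stronger readings that a reader might infer. The first is that the trial cannot show infusion reactions at all; the detection routes above rule that out for symptomatic ones. The second is that all treatment-day vital signs are pre-dose; Section 8.2.3 leaves them untimed. The Day 1 ordering in Section 8.2.2 does not settle the matter either, since the same list includes draws during the infusion. The third is that no active drug is circulating at pre-dose. The half-lives are for intact peptide only, Section 3.3.3 says at least one fragment is active in mice, and its report of fragments detected in human plasma for up to 120 minutes is not a half-life.

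What remains is narrower. Adverse event review and clinically indicated tests depend on someone noticing something. A brief, symptomless change would not prompt them, and in patients with acute respiratory illness an abnormal pulse or respiration rate is easily attributed to the disease. Paired, timed values compared with placebo would separate the two.

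**Conclusion.** The point holds in limited form. Day 3 ECGs and vital signs, and those at EOT under footnotes c and e, are taken when intact peptide is essentially gone: about 54 to 105 mean half-lives after the previous infusion in the usual case, and no more than about 0.3% left in the least favourable case examined. Other treatment-day vital signs are untimed, and nothing scheduled is tied to the infusion. The ECG and vital-sign tables are therefore weak evidence on transient, asymptomatic effects at peak, and a null result should not be presented as reassurance on them.

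This rests on the Section 3.3.6 half-lives carrying over to these patients, on exponential decline, and on intact peptide being the relevant exposure. Nothing in the documents indicates that a haemodynamic or ECG effect exists; the finding concerns what the schedule can show.

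Two inconsistencies need correction regardless: EOT timing (Section 8.2.5 against footnotes c and e) and blood pressure position (supine against sitting), which lets change from baseline mix positions. The change is worth making because it is cheap, but it is not a bar to running the trial.

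**What to change.** Amend footnotes c, e and f and Sections 7.3.2.4 and 8.2.2 to 8.2.6 as follows.

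1. Keep the Day 1 pre-dose ECG and vital signs as baseline.
2. Time the Day 3 and EOT ECGs to the existing end-of-infusion (2 h) blood draw.
3. Record pulse, blood pressure, respiration and temperature pre-dose and at the end-of-infusion draw on Days 1, 3 and EOT. The 1 h draw is optional.
4. In Section 9.3.4.3 and the SAP, tabulate the same-day paired change by arm.
5. State one body position throughout.
6. Reconcile the EOT definition in Section 8.2.5 with footnotes c and e.

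**Cost.** An amendment to the footnotes and eCRF time fields. The number of ECGs is unchanged. Each patient has three extra sets of vital signs (one on each of three days), or six if the 1 h draw is used, at contacts that staff already attend: a few minutes of nursing time each. The real loss is the pre-dose ECG on Day 3 and at EOT, and with it a like-for-like comparison with the pre-dose baseline for persistent effects.

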8.2 Study Visits

8.2.1 Screening (Day 1a)

- Obtain written informed consent from the patient
- Assign screening number
- Review Inclusion/Exclusion criteria with the patient
- Collect demographics and medical history
- Document concomitant drugs, including drug name, dose, and frequency
- Urine pregnancy test for female patients of child-bearing potential
- Perform physical examination including respiratory exam
- Laboratory tests including hematology, biochemistry, coagulation, and urinalysis
- 12-lead ECG
- Measure vital signs, including blood pressure (sitting), pulse rate, body temperature, respiration rate, actual body weight (kg), and height (cm)
- Swab nasal, throat, sputum, or lower respiratory tract source for SARS-CoV-2.
- Calculate eGFR

8.2.2 Baseline Visit (Day 1b)

- Obtain chest x-ray
- Collect blood samples (5 mL each) at Baseline prior to start of drug infusion, at one hour post start of infusion, and end of the daily 2-hour drug infusion for PK, cytokines, and antibody analysis. Prepare the samples per Section 7.3.2.2.
- Review and record any TEAEs
- Complete the (1) Berlin Definition (Appendix 3), (2) SOFA score (Appendix 4), (3) modified Medical Research Council Dyspnea Scale (Appendix 5), and (4) APACHE II score (Appendix 6) pre-dose.
- Randomize the patient
- Administer IV drug over 2 hours (after completion of all other assessments and procedures on Day 1)

8.2.3 During Treatment Period (Days 1, 2, 4 – 14 (maximum))

- Document concomitant drugs, including drug name, dose, and frequency

- Perform physical examination including respiratory exam
- Measure vital signs, including blood pressure (sitting), pulse rate, body temperature, respiration rate, and actual body weight (kg) daily or as clinically indicated – note: no need to document height.
- Administer IV drug over 2 hours
- Review and record any TEAEs.

8.2.4 During Treatment Period (Day 3 and EOT, and when clinically indicated)

- Document concomitant drugs, including drug name, dose, and frequency
- Perform physical examination including respiratory exam
- Obtain chest x-ray on Day 3, in the event of clinical improvement, and at EOT, and when clinically indicated
- 12-lead ECG
- Laboratory tests including hematology, biochemistry, coagulation, and urinalysis on Day 3, EOT, and if clinically indicated
- Measure vital signs, including blood pressure (sitting), pulse rate, body temperature, respiration rate, and actual body weight (kg) daily or as clinically indicated – note: no need to document height.
- Calculate eGFR
- Administer IV drug over 2 hours
- Collect blood samples (5 mL each) at mid-point and end of the 2-hour drug infusion for PK and biomarker analysis. Prepare the samples per Section 7.3.2.2.
- Review and record any TEAEs
- Swab nasal, throat, sputum, or lower respiratory tract source for SARS-CoV-2 on Days 4, 7, 10, and 14 (if necessary).
- Complete the (1) Berlin Definition (Appendix 3), (2) SOFA score (Appendix 4), and (3) modified Medical Research Council Dyspnea Scale (Appendix 5), and (4) APACHE II score (Appendix 6; only if clinically indicated).

8.2.5 End of Treatment (EOT)

The EOT visit refers to the completion of the last dose of study drug. All study assessments outlined during the Treatment Period are to be performed. For a complete list of assessments, refer to the Study Flow Chart.

8.2.6 End of Study (Day 28 EOS ± 3 days)

- Document concomitant drugs, including drug name, dose, and frequency
- Perform physical examination including respiratory exam
- Laboratory tests including hematology, biochemistry, coagulation, and urinalysis, and antiviral antibodies (IgG, IgM, IgA)
- Collect blood sample in the morning for biomarker analyses. Prepare the samples per Section 7.3.2.2.
- 12-lead ECG (if clinically indicated)
- Obtain chest x-ray
- Measure vital signs, including blood pressure (sitting), pulse rate, body temperature, respiration rate, and actual body weight (kg)
- Calculate eGFR
- Review and record any TEAEs
- Swab nasal, throat, sputum, or lower respiratory tract source for SARS-CoV-2 if not eradicated on Day 14.
- Complete the (1) Berlin Definition (Appendix 3), (2) SOFA score (Appendix 4), and (3) modified Medical Research Council Dyspnea Scale (Appendix 5), and (4) APACHE II score (Appendix 6) on Day 28 (EOS).
- Record healthcare resource utilization.

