5.4 Selection of Study Population

5.4.1 Inclusion Criteria

Eligible patients must fulfill the following inclusion criteria:

1. Male or female hospitalized patients between 18 and 80 years of age at time of consent.
2. Clinical and laboratory diagnosis of COVID-19 infection. Patients must be positive for the SARS-CoV-2 by Real-Time Reverse Transcriptase (RT)-PCR Diagnostic Panel or have an existing complication secondary to SARS-CoV-2 infection which was positive within 2 weeks of entry into the study. Further, patients must have at least two of the following three symptoms:
 - Fever (oral temperature $\geq 100.4^{\circ}\text{F}$ [$> 38^{\circ}\text{C}$]) with or without chills
 - Dyspnea or difficulty breathing (≥ 2 on mMRC dyspnea scale)
 - Nonproductive cough (Stokes *et al*, 2020),
 - Or other signs and symptoms of established complications to SARS-CoV-2 infection (*e.g.*, coagulopathy, cardiomyopathy, acute kidney injury [AKI], and/or acute liver injury) within the limits of Exclusion Criteria #8.
3. Patients must present with moderate to severe illness as defined below:
 - Moderate illness: Patients who have evidence of lower respiratory disease by clinical assessment or imaging and an oxygen saturation (SpO_2) $> 93\%$ on room air at sea level
 - Severe illness: Patients who have a respiratory frequency > 30 breaths per minute (bpm), $\text{SpO}_2 \leq 93\%$ on room air at sea level, ratio of arterial partial pressure of oxygen to fraction of inspired oxygen ($\text{PaO}_2/\text{FiO}_2$) < 300 , or lung infiltrates $> 50\%$ (COVID-19 Treatment Guidelines Panel, 2020).
4. APACHE II score < 20 or establishment of survivability of the patient beyond 48 hours

following randomization.

5. Therapies which have been shown to be beneficial and are included in standard-of-care COVID-19 treatment guidelines (e.g., those of WHO or NIH, or institutional guidelines) are permitted.

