7.1.2 Secondary Efficacy Endpoints

- All-cause mortality

- The presence and severity of ADRS as an ordinal outcome of the proportion of patients who have none, mild, moderate, or severe ARDS
- Time to each of mild, moderate, and severe ARDS
- The number of ventilation-free days and ECMO-free days
- Time on nasal canula or oxygen mask
- Length of stay in ICU and hospital (admission to discharge)
- Virologic clearance rate
- Worst PaO₂/FiO₂ ratio following enrollment
- Change in PaO₂/FiO₂ ratio
- Vasopressor-free days
- Change from maximal radiographic damage to EOT
- Change in baseline mMRC score
- Change in APACHE II score
- Proportion of patients with extrapulmonary organ dysfunction using the daily SOFA score
- Change in liver function tests (ALT, AST, total bilirubin)
- Change in renal function tests (SCr, eGFR)
- Change in hs-troponin levels
- Change in ACT, aPTT, and/or PT/INR values
- Change in antiviral IgG, IgA, and IgM levels.

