9 STATISTICAL METHODS PLANNED AND SAMPLE SIZE

9.1 Determination of Sample Size

The sample size (n=60) was determined based on medical judgement and a desire to assess safety in a limited number of patients, prior to further study and patient availability: 30 patients (active) and 30 patients (placebo).

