9.3.2 Efficacy Analyses

The primary efficacy endpoint is the proportion of subjects alive and free of respiratory failure (*e.g.*, need for non-invasive or invasive mechanical ventilation, high flow oxygen (≥ 6 L/minute), or ECMO) and free of the need for continued renal replacement therapy (RRT) on Day 28. The need for continued RRT at Day 28 will be defined as either dialysis in the past 3 days (Day 26, 27, or 28) or an eGFR on Day 28 <10 mL/min/1.73 m².

Analyses for the primary and the key secondary endpoints will be performed on the FAS and PP populations, with the analysis on the FAS as the primary analysis; all other efficacy endpoints will be analyzed on the FAS population only.

Time to event variables will be summarized using Kaplan-Meier survival curves and compared between treatment groups using either Log-rank tests or Cox's Proportional Hazard model adjusting for baseline covariates, as necessary. For continuous variables assessed at multiple time points a Mixed Model Repeated Measures (MMRM) approach will be used or Analysis of Covariance (ANCOVA) if assessed at a single time point post-baseline. For categorical endpoints Cochran-Mantel-Haenszel (CMH) methods will be used, or a logistic regression approach, in the case of continuous covariates.

Additional details regarding precise endpoint definitions (including transformations, as applicable), analysis model specifications and alpha-level control for primary and important secondary endpoints associated with multiplicity will be provided in the SAP, to be finalized prior to unblinding the study.

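### The end-of-study SARS-CoV-2 swab is skipped for patients judged eradicated on Day 14, contradicting the flow chart and leaving false negatives or returns to positive undetected.

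*Combined protocol and SAP*

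**What the plan says.** The endpoint is named in Section 7.1.2, and also in the Synopsis and Section 4.2.2, simply as "Virologic clearance rate". No definition, time point, denominator or confirmation rule is given. Section 9.3.2 leaves to the SAP "Additional details regarding precise endpoint definitions (including transformations, as applicable), analysis model specifications", and the document as supplied contains no SAP text that provides them.

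The swab schedule appears in several places, and they do not agree:

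- **Section 8.1, footnote g:** "Swabs (nasal, throat, sputum, or lower respiratory tract) at Screening, Day 3, EOT, and EOS". The EOS swab is unconditional, and the EOT column is headed as variable in timing.
- **Synopsis and Section 5.1:** SARS-CoV-2 tests on Day 1, Day 3, at EOT and at EOS, again without a condition at EOS.
- **Section 8.2.4:** "Swab nasal, throat, sputum, or lower respiratory tract source for SARS-CoV-2 on Days 4, 7, 10, and 14 (if necessary". The heading of that section nevertheless refers to Day 3 and EOT.
- **Section 8.2.6:** "Swab nasal, throat, sputum, or lower respiratory tract source for SARS-CoV-2 if not eradicated on Day 14".

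Entry has two routes in Section 5.4.1. One is "Patients must be positive for the SARS-CoV-2 by Real-Time Reverse Transcriptase (RT)-PCR Diagnostic Panel". The other is to "have an existing complication secondary to SARS-CoV-2 infection which was positive within 2 weeks of entry into the study".

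**The concern.** Section 8.2.6 is a data-collection rule. A site that follows it takes no further swab from a patient judged eradicated on Day 14. Three things follow.

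1. A Day 14 false negative stays in the data, because the one later swab that could contradict it is not taken. A return to positive between Day 14 and EOS is missed in the same way.
2. EOS virology is available only in patients who were still positive. The analyst must either carry the Day 14 result forward as clearance or work with a group selected for slow clearance.
3. The rule needs a Day 14 result that may not exist. On the flow chart a Day 14 swab is taken only if EOT happens to fall on that day, and Section 5.3 lets dosing end earlier.

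The SAP can define clearance later, but no definition recovers swabs that were never taken. If error is equal in the two arms, the extra false clearances pull a true difference towards zero.

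**Working it through.** **Is there a figure to reproduce?** No. The protocol states no clearance rate, treatment effect, power or swab error rate for this endpoint. Section 9.1 says "The sample size (n=60) was determined based on medical judgement", so there is no sample-size formula to check either.

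**Assumptions (none is in the documents).**

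- The false-negative rate per swab, f, is 5%, 10%, 20% or 30%.
- Errors are independent between swabs, and there are no false positives.
- Error and number of swabs are the same in both arms.
- One negative on Day 14 is read as eradicated.
- The true difference in clearance by EOS is 15 points.

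**Section 8.2.6 rule.** A patient still infected at EOS is scored as cleared if the Day 14 swab is falsely negative, or if it is positive and the EOS swab is falsely negative:

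F = f + (1 − f)f = 1 − (1 − f)².

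For f = 20%: 1 − 0.8² = 0.36.

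**Flow-chart rule, EOS swab in everyone.** Clearance means negative at EOS, so F = f. Negative with no later positive, including EOS, gives the same F, because the EOS swab comes last.

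**Effect on the difference.** In each arm the observed rate is p + (1 − p)F. Subtracting one arm from the other gives observed difference = (1 − F) × true difference, whatever the underlying rates. For f = 20%: 0.64 × 15 = 9.6 points, against 0.80 × 15 = 12.0 points.

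| f (assumed) | F, Section 8.2.6 | F, EOS in all | 15 points observed as, Section 8.2.6 | 15 points observed as, EOS in all |
|---|---|---|---|---|
| 5% | 10% | 5% | 13.5 | 14.3 |
| 10% | 19% | 10% | 12.2 | 13.5 |
| 20% | 36% | 20% | 9.6 | 12.0 |
| 30% | 51% | 30% | 7.4 | 10.5 |

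**Dependence between swabs.** The excess of false clearances under Section 8.2.6 is f − P(both swabs falsely negative). With independent errors P(both) = f², so the excess is f(1 − f): about 5, 9, 16 and 21 percentage points for the four values of f. If a patient who is missed once is always missed, P(both) = f and the excess is zero. Positively correlated errors lie between these limits.

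**Denominator.** The second entry route can admit a patient whose screening swab is already negative. Without a restriction to patients positive at baseline, such a patient could count as cleared on entry. Section 8.2.1 takes a screening swab, so the restriction can be applied.

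**The case against.** The strongest reply is that endpoint definitions are expressly left to the SAP, that this is one item in a long list of secondary endpoints in a 60-patient proof-of-concept study, and that the drug targets neutrophil adhesion and is not presented as an antiviral. Much of this stands. Even with a perfect test, 30 per arm gives only about 35% power for an assumed 50% against 70%. The reply does not reach the collection rule: the SAP can choose a definition but cannot supply missing EOS swabs, and the contradiction between Sections 8.1 and 8.2.6 remains whatever the SAP says.

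A reader might infer more, namely that the protocol counts any single negative swab, from any of the four permitted sources, as clearance. With the three post-baseline swabs of the flow chart, that would give false clearance of 14%, 27%, 49% or 66% at the four error rates. The documents do not support this. Neither clearance nor *eradicated* is defined. Section 8.2.4 lists several on-treatment swabs, so *eradicated* could mean consecutive negatives. A rule of any negative at any time appears nowhere.

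Nor is shrinkage assured. EOT timing varies and the on-treatment swabs are conditional, so the number of swabs could differ by arm and bias could run in either direction.

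It is also tempting to require a confirming negative and the same specimen type as at baseline. Both have a price. On the flow chart, clearance first seen at EOS could not be confirmed. Sputum may also be unobtainable, given that nonproductive cough is one of the entry symptoms.

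**Conclusion.** The point holds as a conflict between sections with a consequence for data collection. Section 8.2.6 contradicts the unconditional EOS swab in the Synopsis, Section 5.1 and Section 8.1. It relies on a Day 14 swab that the flow chart does not schedule, and it leaves later status unmeasured in patients called eradicated.

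The size depends on an error rate that the documents do not give. Under the stated assumptions, the loss from an assumed 15-point difference, compared with swabbing everyone at EOS, is about 0.7 points at 5% error (15 × 0.05 × 0.95) and about 3.2 points at 30% (15 × 0.30 × 0.70). It would be smaller if errors are correlated within patients. Returns to positive are also missed, but nothing in the documents allows their number to be estimated. The amendment is worth making because it is cheap and the swabs cannot be recovered afterwards. It does not bear on the primary endpoint.

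**What to change.** 1. In Section 8.2.6, delete the condition attached to the EOS swab and take the swab in every patient, as Section 8.1 already schedules.
2. Reconcile Sections 8.1, 8.2.4 and 8.2.6 to a single list of swab days.
3. In the SAP, analyse clearance in patients who are swab-positive at baseline, as negative at EOS or as negative with no later positive, including EOS. State how missing EOS swabs are handled, and treat death as Section 9.3.7 requires.
4. Record the specimen type of each swab on the eCRF. A second confirming negative and matching to the baseline specimen type can be sensitivity analyses but should not be required.

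The cost is a wording change, one eCRF field and some additional swabs compared with Section 8.2.6, at a visit where blood samples and a chest x-ray are already planned. Reported clearance rates may be lower.
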